36.	Partial Waiver of Consent for Screening/Recruitment	25
37.	Partial Waiver of HIPAA Authorization for Screening/Recruitment.....	26
38.	Waiver of Documentation of Consent	26
39.	Alteration of Consent.....	27
40.	Full Waiver of Consent/Parental Permission.....	28
41.	Full Waiver of Consent/Parental Permission (Public Benefit or Service Programs)	
	29	
42.	Full Waiver of HIPAA Authorization (Checklist).....	29
43.	Other Waiver Types (Checklist).....	30

44.	Vulnerable Populations (Checklist).....	30
45.	Medical Devices (Checklist).....	36
46.	Export Control (Checklist)	37
47.	Data Transfer/Sharing (Checklist).....	37
48.	Specimen Transfer/Sharing (Checklist).....	38

1. Objectives

1.1. Describe the purpose, specific aims, or objectives.

Our long-term goal is to develop a mindfulness-based intervention (MBI) program that significantly decreases stress/burnout and increases belongingness and connectedness among nurse faculty and staff. The overall objective of this pilot project, which is the next step in toward achievement of our long-term goal, is to examine the feasibility and preliminary efficacy of MBIs as an intervention for University of New Mexico (UNM) Health Sciences Center (HSC) nurse faculty and staff. Our central hypothesis is that this MBI intervention will improve the psychosocial outcomes (sense of belonging) and physiological outcomes (HRV) among HSC nurse faculty and staff. To test our central hypothesis and attain the overall objective, we will pursue the following specific aims:

Aim 1. To evaluate the feasibility and acceptability of MBIs (meditation or yoga) for HSC nurse faculty and staff. Acceptability will be assessed qualitatively from analyses of interviews with participants. Feasibility will be assessed as rates of recruitment, retention, and adherence to the MBI (% training sessions attended).

Aim 2. To evaluate the preliminary effect of MBI (meditation; yoga) in HSC nurse faculty and staff on: psycho-social outcomes (burnout; sense of belonging, stress, anxiety) and physiological outcomes (HRV evaluated by wearable electronics). We hypothesize that: a) psycho-social outcomes will improve post-intervention and b) physiologic measures (HRV) will improve post intervention compared to preintervention.

1.2. State the hypotheses to be tested.

Our central hypothesis is that this MBI intervention will improve the psychosocial outcomes (sense of belonging) and physiological outcomes (HRV) among HSC nurse faculty and staff.

2. Background

2.1. Describe the relevant prior experience and gaps in current knowledge.

Background: Nurses are the foundation of health care in the United States (US). Critically, **there is a growing shortage of academic nurse faculty resulting in limited capabilities to enroll future nurses and thus increase the nursing workforce.** Factors attributed to this shortage include stress and burnout,¹⁻³ lack of collegiality and non-inclusive environment.⁴ These factors lead to significant adverse behavioral, psychological and physiological outcomes.^{1,5} Staff, who are critical to the foundation for learning and innovation in academic nursing,⁶ likely experience similar outcomes.⁷ Notably, the American Association of Colleges of Nursing (AACN; 2024) states a sense of belonging is imperative for successful achievement of academic nursing's mission and priorities which focus on preparing the next

generation of nurses. A sense of belonging goes beyond the subjective feeling of connectedness with a community to a sense of a shared mission and ownership of common outcomes. There is emerging literature surrounding the role of faculty and staff in increasing belonging among students as well as strategies for leaders to create and sustain a culture of belonging. **However, a notable gap in the science is the absence of clinical trials examining the integration of interventions, such as mindfulness-based interventions (MBI), aimed at improving a sense of belonging and connectedness in academic nursing faculty and staff.** This study addresses this critical gap by examining the effect of MBIs on psychosocial and physiological outcomes in faculty and staff, thus directly addressing the number one recommendation from the AACN Leading Across Multidimensional Perspectives (LAMP) Culture and Climate survey to increase belongingness through community connectedness and cohesion.

2.2. Describe any relevant preliminary data.

Preliminary Data: The AACN LAMP Culture and Climate Survey was developed to assess the experiences of students, faculty and staff at nursing schools across the nation.⁷ The survey provides a means to gather input from all constituents (students, faculty, staff) regarding what is working well at an organization and where there are opportunities for improvement. Results are grouped into 5 thematic areas: Perceptions of Culture and Climate, Fair Treatment and Observations of Discrimination, Belongingness, Value of Diversity, Equity and Inclusion, and Campus Services and Clinical Training. Of specific interest to this project is the thematic area of Belongingness.

The UNM AACN LAMP Survey was deployed to all University of New Mexico (UNM) College of Nursing (CON) students, faculty, and staff from March 2023 to April 2023. In total, 47 (57%) faculty and 36 (48%) administrators/staff completed the survey. Faculty and staff responded to 10 items focused on perception of connection to others and feelings of isolation. Approximately 28% of faculty reported when they interacted with other people at the CON, they did not feel included. Roughly 30% of faculty reported they felt their campus did not care about them. Thirty-nine percent of faculty reported they felt isolated from others on their campus and 38% reported they lacked a sense of belonging with their campus community. Finally, an alarming 49% of faculty reported feeling like a stranger when they were with other people from their campus.

Answers by faculty and staff to the question “*to improve the campus climate at my nursing program we need to do more of*” included multiple comments related to: 1) “promoting a sense of belonging”, 2) “building community”, and 3) “fostering cohesiveness and collaboration”. Thus justifying the focus of this project.

2.3. Provide the scientific or scholarly background for, rationale for, and significance of the research based on the existing literature and how will it add to existing knowledge.

It is long been established that mindfulness practices like meditation and yoga are associated with positive mental health outcomes.^{8,9} In addition, mindfulness practices are known to support interpersonal relationships.¹⁰ In the workplace, mindfulness practice improves communication, builds a sense of shared goals leading to greater productivity and retention, and helps to decrease burnout.^{11,12} Furthermore, mindfulness practices foster resilience. Mindfulness practices are also associated with improved physiologic function including autonomic nervous system (ANS) function.¹³ Peripheral ANS activity, including cardiac vagal activity (indexed by heart rate variability [HRV]), regulates dynamic fine-tuning of feedback loops between emotion-related brain circuitry and the heart.¹⁴ HRV is known to be a robust biomarker of health, wellness, stress, and the ability to self-regulate.¹⁵ By instructing individuals in MBIs homeostasis in brain-heart feedback loops is promoted leading to autonomic stability.¹⁶ Given the potential impact of MBI to promote individual and workplace wellness, investigation of this intervention to improve wellness in academic faculty and staff is critical.

3. Study Design

3.1. Describe the study design (e.g., observational; randomized placebo-controlled clinical trial, etc.)

This study is a minimal-risk, single site, quasi-experimental study.

3.2. Describe blinding, if applicable

4. Inclusion and Exclusion Criteria

4.1. Describe how individuals will be screened for eligibility.

The UNM CON currently employs 71 faculty and 71 staff. In addition there are nurses who hold appointment with other departments and the UNM hospital. Using convenience sampling we will recruit and enroll 60 participants into two study groups: 1) mindfulness mediation and 2) yoga. Interested study participants will be contacted by study staff and screened to determine study eligibility (See Attachment A). The screener is approximately 1-page in length and takes approximately 5 minutes to complete. The screener includes queries related to inclusion and exclusion criteria. Participants will also complete an Exercise Participation Screening (see Attachment B).¹⁷

4.2. Describe the criteria that define who will be included or excluded in your final study sample, including age. “Age” can be part of a de-identified data set provided ages over 89 are not included. In order to maintain a de-identified classification, all ages over age 89 may be aggregated into a single category of “age 90 or older”. If specific ages over 89 are included, then this would be considered a Limited Data Set.

Inclusion criteria for the study include: 1) 18 years of age or older, 2) in general good health, 3) employed as HSC nurse faculty or staff, 4) reside in the state of New Mexico and able to attend 6 weeks of in-person research sessions, 5) willing to complete research assessments, 6) own a smart phone.

Exclusion criteria for the study include: 1) major medical illness making individual unable to participate in the research.

Additional Screening Criteria: Vigorous-intensity exercise is accompanied by a small risk of cardiovascular complications, however, proper screening minimizes these risks.¹⁷ The American College of Sports Medicine's (ACSM) guidelines are designed to eliminate barriers for an individual to begin a regular exercise program. Additional screening criteria will include completion of the Preparticipation Exercise Participation Screening (See Attachment B).

4.3. Special Populations: Will any of the following populations be included in this study? Indicate specifically whether or not you will include each of the following special populations below.

- Adults unable to consent: Yes No
- Pregnant women: Yes No **or** Not targeted nor is pregnancy screened for
- Minors (individuals who are under the age of 18): Yes No
- Mothers who are minors cannot enroll their child into a research study without the consent of their parent or parents, as applicable. Clarify if applicable.
- Minors in foster care must be excluded from research per NM state law. Please state minors in foster care will be excluded, if applicable.
- Minors that are wards of the state must have additional safeguards met; Please consult with the HRPO if not excluding minors who are wards of the state. Otherwise state that wards of the state will be excluded.
- Prisoners Yes No; If yes, please contact HRPO; Inclusion of prisoners requires approval from the Office for Human Research Protections (OHRP) and from the NM Corrections Department.
- Non-English speakers Yes No; If yes, please clarify specific languages enrolling: **Note:** State congruently in section 25. Consent Process, subsection, Subjects not fluent in English.

4.4. Indicate if you excluding any particular populations (e.g., women, children, persons not fluent in English, a particular racial or ethnic group, etc.) and provide justification.

This study excludes individuals under that age of 18 due to the focus on adult faculty and staff employed at the UNM HSC. We will exclude pregnant individuals due to specific activity modifications that would be required to assure the safety of these individuals during yoga. We will not recruit individuals unable to provide written consent in English.

4.4.1. If excluding pregnant women, please indicate how investigators will screen for pregnancy.

5. Number of Subjects

5.1. If this is a multicenter study, indicate the total number of subjects to be accrued across all sites.

N/A. this study is not a multicenter study.

5.2. Indicate the number of subjects to be recruited at this site.

We will enroll 60 faculty and staff in this study. Once we have enrolled 30 participants, we will waitlist individuals for a second six-week intervention session after the completion of the first session. This will result in a possible enrollment 60 individuals.

5.3. Provide sample size justification

The planned overall sample size of 30 is consistent with recommendations for pilot studies seeking to build evidence in the context of medium effect size differences between two groups.¹⁸

6. Study Timelines

6.1. Describe:

- *The duration of an individual subject's participation in the research*
- *The duration anticipated to enroll all subjects*
- *The expected duration for the investigators to complete the study (complete analysis)*

Participants will be enrolled until the allotted 30 participants for the first 6 weeks of the study is reached. The study is comprised of a pre-intervention assessment, followed by 6 weeks of meditation/yoga attendance (twice/week). Upon completion of the 6-week intervention, participants will complete a post intervention assessment (See Table 1.).

Table 1. Study Timeline	Months									
	1	2	3	4	5	6	7	8	9	10
Prepare research and data management tools.		→								
Session 1										
Recruitment		→								
Intervention		→	→							
Data Collection		→	→							
Preliminary Data Analyses				→						
Session 2										
Intervention				→						
Data Collection				→						
Analyses					→					
Prepare R01 proposal										→
Dissemination										→

7. Study Endpoints: Primary endpoint(s) are typically efficacy measures that address the main research question. Secondary endpoints are generally not sufficient to influence decision-making alone, but may support the claim of efficacy by demonstrating additional effects or by supporting a causal mechanism.

7.1. *Describe the primary and secondary study endpoints.*

Primary outcomes of interest of this study include the feasibility and acceptability of mindfulness-based interventions (MBI) (Aim 1). We will also examine the preliminary effect of these interventions on psychosocial outcomes (primary: sense of belonging; secondary: burnout, stress) and physiologic outcomes (HRV) (Aim 2).

7.2. *Describe any primary or secondary safety endpoints.*

This is a minimal risk study.

7.3. *Describe any exploratory endpoints.*

N/A There are no anticipated exploratory endpoints.

8. Research Setting

8.1. *Describe the sites or locations where your research team will conduct the research.*

Potential participants will be recruited from the UNM HSC. The UNM HSC currently employs 71 faculty and 71 staff in the CON, plus nurse faculty and staff in other HSC programs. Study personnel will conduct all screenings in the private clinical research rooms housed within the CON Research Laboratory suite.

8.2. *Identify where your research team will identify and recruit potential subjects.*

Potential participants will be identified and recruited from the UNM CON.

8.3. *Identify where research procedures will be performed including any laboratory analytics*

Informed consent and research visit interviews will occur in private clinical research rooms housed within the UNM CON Research Laboratory suite. Questionnaires will be administered via secure REDCap survey. Garmin devices will be distributed and/or collected after completion of questionnaires. Meditation and yoga sessions will occur in the Collaborative Research Space housed within the CON Research Laboratory suite.

8.4. *Describe the composition and involvement of any community advisory board*

N/A, this study does not involve a community advisory board.

8.5. *For research conducted outside of UNM HSC and its affiliates describe:*

- *Site-specific regulations or customs affecting the research*
- *Local scientific and ethical review structure/requirements (Note: include any approvals (IRB, facility, or other) with your submission)*

N/A, this is a single site study.

9. Resources Available

9.1. Describe the qualifications of the PI and study staff (e.g., training, experience, oversight) as required to perform the research. When applicable describe their knowledge of the local study sites, culture, and society.

The PI, [name], has been a registered nurse for the past 37 years. In addition, [name] is an Associate Professor in the UNM CON and has been a faculty member of the UNM CON since 2013. She has extensive experience in the evaluation of stress and collection of both biological and behavioral research data. Additionally, [name] has successfully conducted research employing mobile ecological momentary assessment.^{19,20} [name] is also a Registered Yoga Teacher (RYT) 200 and will lead the yoga intervention.

[name] (Co-Investigator) has been a registered nurse for the past 35 years, a professor for 14 years and at the UNM CON for 4 years. She is part of a fellowship in contemplative medicine. In addition, she has 15 years of mindfulness practice and is an ordained Soto Zen Priest.

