Feasibility of recruitment: The UNM CON currently employs 71 faculty members and 71 staff members with additional nurse faculty in other HSC schools and colleges and the hospital. The planned overall sample size of 30 per cohort is consistent with recommendations for pilot studies seeking to build evidence in the context of medium effect size differences between two groups.¹⁸ Furthermore, objectives of pilot studies include assessment of recruitment and retention rates.¹⁸

The UNM College of Nursing is housed in the College of Nursing/College of Population Health Building. The UNM College of Nursing has a state-of-the-art Research Laboratory suite that includes private clinical research rooms as well as a large collaborative research space to conduct the intervention.

This is a minimal risk study that is not expected to have adverse psychological or medical consequences for participants. However, if needed there are providers available for referral and referral procedures are described below in Section 18 - Risks to Subjects.

Prior to beginning recruitment and enrollment, all study personnel will be trained on the protocol as well as consent and interview procedures for the study. All study personnel will have completed training for the ethical conduct of research. Study coordinators will routinely monitor the approved study team member list to ensure all team members remain current in their training.

10. Prior Approvals

- 10.1. *Describe any approvals that will be obtained prior to commencing the research. (e.g., school, external site, funding agency, laboratory, radiation safety, or biosafety approval.)* N/A
- 10.2. *Upload the required Departmental Review Form signed by your Department Chair (or authorized designee if the PI is the Department Chair) into Huron IRB under “supporting documents.” The signed, required Departmental Review form has been uploaded under “supporting documents”.*

10.3. If a study includes ionizing radiation, the Radiation Safety Attachment (HUS-FORM_1) must be uploaded (attached) in Huron IRB with your submission. The consent should include radiation exposure information in the Risks section.

N/A

10.4. If applicable to the study, include the signed “Biological Specimens” and/or “Drug Attachment” in Huron IRB with your submission.

N/A

11. Multi-Site Research

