The UNM CON currently employs 71 faculty and 71 staff and the HSC has additional nurse faculty and staff. We will employ a quasi-experimental design to assess feasibility, acceptability, and preliminary efficacy of MBIs (meditation; yoga) to increase a sense of belonging and connectedness in academic nursing faculty and staff. Using convenience sampling we will recruit and enroll 60 participants in to two study groups: 1) mindfulness mediation and 2) yoga. Interested study participants will be contacted by study staff and screened to determine study eligibility (See Attachment A). The screener is approximately 1-page in length and takes approximately 5 minutes to complete. The screener includes queries related to inclusion and exclusion criteria. Participants will also complete an Exercise Participation Screening (see Attachment B).¹⁷

Pre-data collection:

We will assign 15 individuals to each condition. Across both conditions, all participants will participate in one baseline assessment/training session, 6 weeks of MBIs (participants will be required to attend 2 sessions per week), and a post-intervention assessment session. Following screening for inclusion/exclusion criteria, eligible participants will complete the BEING Mindful Exercise participation screening. Eligible participants will provide informed consent.

After informed consent is obtained, research staff will allocate individuals to meditation vs yoga on 1:1 basis. If an individual is unable to participate in the yoga arm based on the BEING Mindful Exercise participation screening, they will be assigned to meditation and the next two participants will be assigned to yoga.

All participants will be given an anonymous study ID number once they are enrolled in the study. The only link between the study ID number and any identifier will be stored in a secure N:\Research-Studies network drive, in a folder to which only the investigators will have access. Any link between the study ID and identifiers will be destroyed when data analysis is complete.

Once we have enrolled 30 participants we will waitlist individuals for a second six-week intervention session after the completion of the first session. This will result in a possible enrollment 60 individuals.

12.3. For studies that collect existing or prospective data, describe the source of information, whether collected prospective or retrospectively.

Data collection:

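### Section 5.3 gives the overall sample size as 30, which is the size of one cohort; the planned total elsewhere is 60, and that total has no statistical or precision rationale

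*Combined protocol and SAP*

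**What the plan says.** The combined protocol and SAP states the study's size in several places.

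- **Section 5.3 (sample size justification):** "The planned overall sample size of 30 is consistent with recommendations for pilot studies". The support is a citation to recommendations for pilot studies looking at medium differences between two groups.
- **Section 9 (feasibility of recruitment):** almost the same sentence with the same citation, but reading "The planned overall sample size of 30 per cohort is consistent with recommendations".
- **Section 4.1:** "Using convenience sampling we will recruit and enroll 60 participants into two study groups".
- **Section 12.2:** "Using convenience sampling we will recruit and enroll 60 participants in to two study groups". The subsection then assigns 15 people to each of the two conditions, without saying whether this is per cohort or overall. Section 12.5 repeats the 15 without that qualifier.
- **Section 5.2:** "We will enroll 60 faculty and staff in this study". It then explains that after 30 enrolments further people are waitlisted for a second six-week session, and ends "This will result in a possible enrollment 60 individuals".
- **Section 6.1:** "Participants will be enrolled until the allotted 30 participants for the first 6 weeks of the study is reached". Table 1 shows a Session 1 and a Session 2.

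Section 7.1 makes feasibility and acceptability primary: "Primary outcomes of interest of this study include the feasibility and acceptability of mindfulness-based interventions". Section 13.1 (Aim 1) plans 95% confidence intervals for recruitment, retention and completion of all training sessions. Section 13.2, the power analysis item, has no text under it.

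**The concern.** The section whose purpose is to justify the number of participants gives an overall number that disagrees with the enrolment plan by a factor of two. One rationale and one citation are attached to two different quantities, 30 overall and 30 per cohort.

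Two practical questions follow. If only the first cohort runs, has the study met its target or reached half of it? Section 5.3 suggests the first and the opening of 5.2 the second, while the later word 'possible' in 5.2 allows either. In a pilot that counts recruitment among its feasibility measures, that should be settled beforehand. And on how many people will the retention and session-completion rates be based? Section 13.1 gives no number, so the reader must go back to section 5, where the two figures conflict.

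**Working it through.** **1. Counts.** Inputs: 15 per condition (12.2, 12.5), two conditions (4.1, 12.2), two sessions (5.2, 12.2, Table 1).

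- Per cohort: 15 × 2 = 30. This agrees with sections 6.1 and 9.
- Total: 30 × 2 = 60. This agrees with sections 4.1, 5.2 and 12.2.
- Per condition over both cohorts, if both fill: 15 × 2 = 30.
- Section 5.3 as written: 30 overall, and 30 / 60 = 0.5 of the planned total.

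Every figure except the one in 5.3 fits a single scheme of 30 per cohort and 60 in total. The 15 per condition fits only if it is read as applying to each cohort. Read as an overall number it gives 30, against the 60 planned earlier in the same subsection.

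**2. Can the 30 or the 60 be derived?** No. The plan gives no numerical effect size, standard deviation, significance level, power, dropout rate or target interval width for either number. The 30 rests on a citation whose content is not available here, so whether that source supports 30 or 60 is not judged. The 60 comes only from running two sessions of 30.

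**3. What the choice of N does to a planned estimate.** Retention is the clearest case, because its denominator is the number enrolled. The plan gives no expected retention, so 80% is assumed, with a range of 70% to 90%. It names no interval method either; the exact (Clopper-Pearson) interval is used here. For x retained of n:

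- lower limit = 2.5% quantile of Beta(x, n − x + 1)
- upper limit = 97.5% quantile of Beta(x + 1, n − x)

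| Assumed retention | 60 enrolled | 30 enrolled |
|---|---|---|
| 70% | 42/60: 0.568 to 0.812 | 21/30: 0.506 to 0.853 |
| 80% | 48/60: 0.677 to 0.892 | 24/30: 0.614 to 0.923 |
| 90% | 54/60: 0.795 to 0.962 | 27/30: 0.735 to 0.979 |

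At 80% the interval is about 22 percentage points wide with 60 (0.892 − 0.677 = 0.215) and about 31 with 30 (0.923 − 0.614 = 0.309).

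**The case against.** The strongest reply is that the document largely resolves the conflict itself. Section 9 supplies the missing words, 5.2 and 12.2 explain the two sessions, and Table 1 shows them. Section 5.2 stands directly above 5.3 and opens with 60, so a careful reader is unlikely to leave section 5 believing that the whole study is 30. The 15 per condition in 12.2 stands shortly before the statement that a second session follows the first 30. All of this holds, and it makes the matter an inconsistency of wording rather than a failed calculation. It does not make 5.3 correct, and it does not settle whether 60 is a target or a maximum.

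Three stronger readings are tempting and are not supported.

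- **That 60 has no basis at all.** Sections 5.2 and 12.2 give it an operational one, two sessions of 30, and section 9 offers the cited recommendation for each cohort. Only a statistical or precision justification of the total is missing.
- **That the precision of every primary outcome turns on 30 or 60.** Acceptability is assessed qualitatively from interviews. A recruitment rate would naturally be taken over those approached or eligible, not over those enrolled. Only retention and session completion scale directly with the enrolled number.
- **That the mention of a medium effect in 5.3 is a failed power claim.** The plan claims no power. Section 13.1 seeks estimates for a later power analysis, treats Cohen's d as descriptive and plans no confidence interval for it. A power figure or an interval width for d would need inputs that the plan does not state, and the inconsistency does not depend on them.

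**Conclusion.** The point stands in a limited form. The overall sample size in section 5.3 is wrong as written: 30 is the cohort size and the planned total is 60. This follows from the document's own statements and needs no assumption. The total has an operational origin but no statistical or precision justification, the number per condition in 12.2 and 12.5 fits one cohort only, and 5.2 describes 60 both as definite and as possible.

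The effect on the planned retention estimate is moderate. With 30 rather than 60, the exact 95% interval at 80% retention widens from 68% to 89% to 61% to 92%. These intervals rest on the assumed retention, on the exact method, and, for 60, on both cohorts filling and being pooled. The correction is worth making because it concerns the section that exists to justify N and is almost free; it does not call the design into question.

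**What to change.** - **Section 5.3:** keep the cited rationale and state the size as 30 per cohort (15 per condition) and 60 in total over two cohorts (30 per condition if both fill).
- **Section 5.3, short rationale for the total (optional):** give the expected precision of the retention rate that 13.1 will report, labelled as an assumption. For an assumed 80% retention, the exact 95% interval is about 68% to 89% with 60 enrolled and 61% to 92% with 30. If a range is wanted, assumed retention of 70% and 90% gives 57% to 81% and 79% to 96% with 60, and 51% to 85% and 73% to 98% with 30.
- **Section 5.2:** say whether 60 is the enrolment target or a maximum, so that it is clear whether a single completed cohort meets the plan.
- **Sections 12.2 and 12.5:** say that the 15 per condition applies in each cohort.

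No power statement and no precision statement for Cohen's d is needed. The cost is a few edited sentences, with no added participants, procedures or analyses.
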